5.2 Study Populations for Analysis

5.2.1 Intention-to-Treat (ITT) Population

The ITT population includes all randomized subjects. Analysis will be done according to the treatment subjects were randomized to. All baseline characteristics will be summarized for the ITT population.

5.2.2 Safety Population

The Safety population will consist of all subjects who received at least 1 HD treatment with AKST1210/Control after randomization. All safety endpoints will be summarized for the Safety population. Analysis will be done according to the actual treatment subjects received.

5.2.3 Evaluable Population

The Evaluable population will consist of all subjects who completed through Week 8, defined as having a week 8 visit. All secondary endpoints will be summarized for the Evaluable population. Analysis will be done according to the treatment subjects were randomized to.

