3.2 Secondary Endpoints

- Feasibility of all procedures, including blinding.
- Tolerability of each column size escalation, as measured by subject compliance with study visit schedule/completion, visit procedures, and subject retention.
- The change in IDH Rate above each subject's Historical IDH Rate for each column size.
- The incidence of IDH leading to de-escalation or discontinuation.
- The incidence of worsening anemia by column size.
- The incidence of anemia leading to de-escalation or discontinuation.
- Change from baseline in levels of b2M at Weeks 4, 8, 12 and end of study (EOS) and evaluation of any differences in the magnitude of change based on column size and duration of treatment with a specific column size.
- Change in Montreal Cognitive Assessment (MoCA) from baseline to EOS.
- Change in cognitive domains as measured with the Cogstate battery (i.e., verbal learning, psychomotor function, visual attention, working memory, executive function, and verbal delayed recall).
- Change in quality of life per the Short-Form Health Survey (SF-36).
- Change in the Patient Health Questionnaire-9 (PHQ-9).
- Change in sleep quality as measured by the Pittsburgh Sleep Quality Index (PSQI).
- Change in fatigue as measured by the Fatigue Questionnaire – Functional Assessments of Chronic Illness Therapy (FACIT).
- Changes from baseline in laboratory test data, vital sign measurements, and electrocardiograms (ECGs).

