5.7 Efficacy Analyses

Efficacy analyses will evaluate the feasibility of conducting expanded studies of AKST1210 in subjects with ESRD-CI who are undergoing HD 3 times per week, and its efficacy. The efficacy analyses will be descriptive only. Except where indicated, efficacy parameters will be summarized using the Evaluable and PP populations. All efficacy data, regardless of population, will be presented in data listings.

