5.7.1 Feasibility of all Procedures

Feasibility of all procedures will be determined by the number of assessments that can be completed by the subject, visits that are completed, dialysis sessions that are completed with the longer dialysis time and the number of times the dialysis session becomes unblinded to treatment. A less than 75% completion by subjects would determine the procedure non-feasible calculated by treatment period and study overall. The percentage of subjects who are missing at each procedure will also be summarized.

5.7.2 Tolerability of Column Size, including Subject Compliance with Visit Completion, Procedures, Subject Retention

The number and percentage of subjects will be summarized by column size (AKST1210 S-15, S-25, and S-35), overall AKST1210 and control for the following:

- Subjects entered into each treatment period
- Subjects who de-escalated to a lower column size in treatment period 3 categorized by reason: IDH only, Anemia only, IDH and Anemia. Anemia is defined as having a hemoglobin (Hgb) lab value of < 9g/dL, Subjects who were discontinued due to treatment or HD
- Subjects who completed all the visits

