5.7.4 Incidence of IDH Leading to De-escalation or Discontinuation

The number and percentage of subjects with any IDH leading to de-escalation or discontinuation from AKST1210/control will be summarized by treatment group and Total.

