5.7.6 Incidence of Anemia Leading to De-escalation or Discontinuation

The number and percentage of subjects with any anemia leading to de-escalation or discontinuation from AKST1210/control will be summarized by treatment group and Total.

5.7.7 Change from Baseline in Levels of b2M, Evaluation of Change Based on Column Size

Blood sampling for b2M concentration will occur at Run-in, during the treatment period, and at EOS. During the treatment period, blood samples will be collected at 3 sample locations (A, B, C, [Figure 2](#)) and at multiple time points prior to dialysis (PTD), at 1 hour, 2 hours, and at the end of dialysis (EOD) at the end of each 4-week treatment (V2.11, V3.11 and V4.11). Detailed collection schedule could be found in [Figure 2](#) and [Table 1](#).

[figure not shown]

Figure 2. The b2M sample locations in the control and the AKST1210 group.

Table 1. Collection schedule of b2M samples

| Study period | Run-in | Treatment period | | | | | | | | | | End of study | |
|-----------------|--------|----------------------|--------|---------|-----|----------------------|--------|---------|-----|----------------------|--------|--------------|---------------|
| Study visit | V1.5 | V2.11 | | | | V3.11 | | | | V4.11 | | | V6 |
| Study week(day) | | Week 4 (D4) | | | | Week 8 (D52) | | | | Week 12 (D80) | | | Week 14 (D96) |
| Column size | | 150 mL column (S-15) | | | | 250 mL column (S-25) | | | | 350 mL column (S-35) | | | |
| Timepoint | PTD | PTD | 1 hour | 2 hours | EOD | PTD | 1 hour | 2 hours | EOD | PTD | 1 hour | 2 hours | PTD |
| Sample location | A | A | A,B,C | A,B,C | A | A | A,B,C | A,B,C | A | A | A,B,C | A,B,C | A |

PTD: prior to dialysis; EOD: end of dialysis. Sample location A is before the AKST1210 column. Sample location B is after the AKST1210 column and before the hemodialyzer. Sample location C is after both the AKST1210 column and the hemodialyzer. In the control group, because there is no AKST1210 column, sample location A is the same as sample location B ([Figure 2](#)).

Three hypotheses will be tested to evaluate the effects of AKST1210 columns on b2M removal, including overall removal after AKST1210 treatment and instantaneous removal during AKST1210 treatment.

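### Retention and IDH/anemia discontinuation endpoints default to subjects with a Week 8 visit, so earlier stops leave both numerator and denominator

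*SAP*

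**What the plan says.** SAP 3.2 lists feasibility, tolerability (including retention), IDH and anemia among the secondary endpoints, for example "The incidence of IDH leading to de-escalation or discontinuation". SAP 5.2.3 then says "All secondary endpoints will be summarized for the Evaluable population", and that population is limited to subjects who "completed through Week 8, defined as having a week 8 visit". SAP 5.7 sets the same default: "Except where indicated, efficacy parameters will be summarized using the Evaluable and PP populations". PP (SAP 5.2.4) is narrower still, since it requires completion of all three treatment periods.

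Sections 5.7.1 to 5.7.6 name no other population. SAP 5.7.2 counts "Subjects entered into each treatment period" and "Subjects who de-escalated to a lower column size in treatment period 3 categorized by reason". SAP 5.7.4 counts subjects with "any IDH leading to de-escalation or discontinuation from AKST1210/control", and 5.7.6 counts those with "any anemia leading to de-escalation or discontinuation from AKST1210/control". Under SAP 5.1, percentages generally use the number in the analysis population of each treatment group. Protocol 10.3 and 10.4.1 also place the secondary endpoints on the Evaluable Dataset.

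**The concern.** These endpoints measure whether subjects stay on treatment, yet the analysis population is selected on having stayed at least to Week 8. A subject who stops for IDH or anemia before then is neither an event nor in the denominator. The secondary objective in SAP 2.2 is to judge the feasibility of expanded studies, and these tables feed that judgement.

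The direction is not fixed. Early IDH or anemia stops make the tables too favourable. Early losses for other reasons shrink the denominator and raise the incidence. Protocol 5.4.2 allows subjects who discontinue before Week 8 to be replaced, so the size of the Evaluable set does not reveal how many stopped.

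**Working it through.** **Plan's own figure.** 10 evaluable per arm / (1 − 0.20) = 12.5, rounded up to 13; 2 × 13 = 26, which matches the stated enrolment. Forward, 26 × 0.8 = 20.8. The sample size is not in dispute.

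**What the default does**
- SAP 5.7.2: having a Week 8 visit implies having entered Periods 1 and 2, so those rows are 100% by construction for overall AKST1210 and for control.
- SAP 5.7.4 and 5.7.6: a stop before any Week 8 visit contributes 0 to numerator and denominator. In PP, any stop before the end of Period 3 is excluded by definition.
- SAP 5.7.1, 5.7.3 and 5.7.5 share the default, but the effect is less direct.

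**Illustrative size.** Event counts are assumed. With 13 treated in the active arm, *m* early losses (of which *e* are IDH/anemia stops) and *l* later events: Evaluable = *l*/(13 − *m*); all treated = (*e* + *l*)/13. Intervals are Clopper-Pearson 95%.

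| Scenario | Evaluable | All treated |
|---|---|---|
| 1 early IDH/anemia stop, no later event | 0/12 = 0% (0 to 26.5) | 1/13 = 7.7% (0.2 to 36.0) |
| 2 early stops, no later event | 0/11 = 0% (0 to 28.5) | 2/13 = 15.4% (1.9 to 45.4) |
| 3 early stops, no later event | 0/10 = 0% (0 to 30.8) | 3/13 = 23.1% (5.0 to 53.8) |
| 3 event-free early losses, 2 later events | 2/10 = 20.0% (2.5 to 55.6) | 2/13 = 15.4% (1.9 to 45.4) |

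**Week 8 retention.** 26 × 0.20 = 5.2, so 5 or 6 lost. If all are early and all 26 were randomised: 21/26 = 80.8% (60.6 to 93.4) or 20/26 = 76.9% (56.4 to 91.0), against 100% in Evaluable.

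**The 75% feasibility threshold (SAP 5.7.1).** The verdict could change only if completion means the share of subjects completing a procedure and early losses complete none. With 6 lost, passing needs 15/20 = 75.0% in Evaluable but 20/26 = 76.9% in all randomised, which is every remaining subject (19/26 = 73.1% fails). With 5 lost, it needs 16/21 = 76.2% against 20/26.

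**De-escalation.** Protocol 10.4.2 includes AEs leading to de-escalation. The SAP's AE section carries forward only discontinuation or withdrawal, the AE action-taken field in protocol 8.4.1 offers only no action or device discontinued, and SAP 5.7.2 counts de-escalation in Period 3 only. A subject de-escalated in Period 2 who leaves before a Week 8 visit is therefore in no SAP summary table as a de-escalation. One who stays to Week 8 is still counted in 5.7.4 or 5.7.6.

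**Conflict within the SAP.** SAP 3.2 lists laboratory tests, vital signs and ECGs as secondary endpoints, but SAP 5.8 analyses them on Safety. The sentence in 5.2.3 therefore cannot apply to every secondary endpoint.

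**The case against.** The strongest reply is that little is lost from the report as a whole. Disposition (SAP 5.3) counts premature withdrawals with reasons. Appendix 17.1 requires every IDH after consent to be recorded as an AE, so IDH after first treatment enters the Safety-set TEAE tables, and IDH causing withdrawal enters SAP 5.8.5.3. Hemoglobin below 9 g/dL is tabulated on Safety (SAP 5.8.6). Protocol 10.4.5 assesses retention without an Evaluable restriction, and listings cover all randomised subjects. All of this stands and limits the harm, but none of it corrects the named endpoint tables.

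Early rule-based stops may also be uncommon. Appendix 17.1 words the rule-based stop as following de-escalation to S-15, which points to Period 2 or later. However, SAP 4.7 and protocol 15.1.2 foresee discontinuation in Period 1, and investigators may stop a subject at any time. Those passages need reconciling, and the frequency cannot be read from the documents.

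IDH and anemia could be called safety endpoints under SAP 5.2.2. But they sit under SAP 5.7, outside the list that opens 5.8, with no override. The table shells are separate and could name another population, but the SAP text does not.

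Three limits are accepted. The event counts are assumptions. The 26 are described as enrolled, so fewer may be randomised. The 100% entry figure holds for whole arms but not for the S-25 row, which depends on escalation.

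**Conclusion.** The point holds. Followed as written, the SAP conditions retention and IDH/anemia discontinuation on reaching Week 8 and so removes part of what these endpoints exist to count. In the illustrations the incidence differs by 7.7 to 23.1 percentage points when early losses are all IDH/anemia stops, and by 4.6 points (20.0 − 15.4) in the other direction when they are event-free. With no early losses the two analyses agree. Retention to Week 8 carries no information in Evaluable. These sizes assume 13 treated in the active arm (26 randomised for retention), with losses before any Week 8 visit. The primary TEAE/SAE analysis is not affected. It should be fixed before unblinding.

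**What to change.** In SAP 5.2.3 and 5.7.1 to 5.7.6:

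1. Analyse the IDH and anemia endpoints (5.7.3 to 5.7.6) in the Safety population.
2. For rows by column size, use as denominator the subjects treated with that size. Plain Safety N would mislead: if 3 of 13 stop on S-15 and 2 have worsening anemia on S-25, the figure is 2/13 = 15.4% on Safety N, 2/10 = 20.0% of those treated with S-25, or 2/8 = 25.0% if only 8 escalate. Show sessions or weeks of exposure beside the 5.7.3 counts: a period has 3 × 4 = 12 sessions, so 1 IDH in 6 sessions equals 2 per 12. SAP 5.7.8 already summarises much of this exposure.
3. Report retention and tolerability (5.7.2) and overall feasibility (5.7.1) in all randomised subjects, with per-period feasibility also among those who entered the period. In 5.7.2, summarise de-escalation whenever it occurs.
4. Keep Evaluable and PP as supportive.
5. Reconcile with SAP 5.2.2 and protocol 10.3/10.4.1, or record the departure from the protocol.

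The cost is SAP wording, different population flags, exposed-subject denominators, a session count and a little more programming. No new data are needed. Some reported figures may become less favourable.

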5.2.4 Per-Protocol (PP) Population

The PP population is a subset of the Evaluable population who completed all of the three (3), 4-week HD treatment periods, and completed the study without any protocol deviations that impact analyses. Such protocol deviations are departures from the approved protocol relating to the conduct of the study which may significantly impact the completeness, accuracy, and/or reliability of the study data or that may significantly affect the rights, safety or wellbeing of study participants. A listing of study subjects with protocol deviations, which would preclude inclusion in the PP population will be provided by the Sponsor prior to database lock. Deviations related to coronavirus disease 2019 (COVID-19) will also be evaluated and provided prior to database lock.

The PP population will be used to support the secondary efficacy endpoint analysis. Analysis will be done according to the treatment that subjects were randomized to.

5.2.5 Subgroup Analyses

Not applicable.

5.3 Subject Disposition and Withdrawals

All subjects who signed the informed consent will be accounted for in Subject Disposition. The following disposition information will be summarized by the number and percentages of subjects:

- Subjects who signed the informed consent, and who comprise the ITT, Safety, Evaluable and PP populations
- Subjects who complete the study or withdraw prematurely along with the reason for discontinuation

A listing of subject disposition and subjects with failed eligibility criteria will be provided.

A listing of Safety subjects excluded from the Evaluable/PP population with the reason for exclusion will be provided.

5.4 Demographics and other Baseline Characteristics

5.4.1 Demographics

Sex, women of childbearing potential (WOCBP), age (in years), race, ethnicity, baseline BMI (kg/m^2) and subjects' highest education level will be summarized by treatment group and Total for the ITT population. BMI (kg/m^2) will be calculated as: $10,000 * \text{weight} (\text{kg}) / \text{the square of height} (\text{cm})$. If height is collected in inches, it will be converted to cm by dividing the value by 2.54. If weight is collected in pounds, it will be converted to kg by dividing the value by 2.205.

The means of continuous demographic variables will be tested using Wilcoxon rank-sum test and the proportions of categorical demographic variables will be

tested using Fisher's Exact test in order to evaluate the effectiveness of the randomization in producing homogeneous pre-treatment groups.

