5 STUDY ENROLLMENT AND WITHDRAWAL

5.1 INCLUSION CRITERIA

In order to be eligible for inclusion, all subjects must meet the following criteria:

1. Male and female subjects, ≥ 40 years of age.
2. b2M level > 20 mg/L.
3. On chronic HD due to ESRD for ≥ 12 months.
4. HD performed using standard HF dialyzers (medium cut-off dialyzers are not acceptable).
5. Score on the MoCA ≥ 16 and ≤ 23 .
6. Life expectancy > 6 months (as determined by the investigator).
7. Body mass index (BMI) ≥ 20 and ≤ 36 .
8. If on medications for cognition (e.g., rivastigmine, galantamine, donepezil, memantine), must be on stable regimen for at least 8 weeks prior to Screening and remain on stable dose for the duration of the study.
9. If on antidepressant medications, must be on stable regimen for at least 8 weeks prior to Screening and remain on a stable dose for the duration of the study.
10. Must be on stable regimens (> 4 weeks) of all treatments for concomitant diseases (e.g., diabetes, hypertension, congestive heart failure).
11. The subject must be able to follow the study protocol, receive the treatment in the established timeframe, and continue during the follow-up interval.
12. The subject must have sufficient visual and auditory acuity to reliably complete all study assessments.
13. Provided a signed and dated informed consent form.

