7.1.1.1.3 Physical Examination

A complete physical examination will be performed at Screening to assess the following organ systems: skin, ENT (ears, nose, and throat), head, eyes, lungs/chest, heart, abdomen, musculoskeletal, extremities, and neurologic and lymphatic systems. The neurological exam will include cranial nerves (fundoscopic exam, pupillary light reflex, extraocular muscles, facial sensation and symmetry, palate and tongue, and head turning and shoulder shrug); muscle strength; reflexes (biceps, triceps, knees, ankles, and plantar); coordination (finger-to-nose, heel-knee-shin); sensory function (light touch and pinprick); and gait. Physical and neurological examination assessments performed within 3 months of the Screening visit need not be repeated. Height will be measured at Screening; weight will be measured at Screening and throughout the study.

7.1.1.1.4 12-Lead ECG

A 12-lead ECG will be performed after the subject has rested quietly for at least 5 minutes in a supine position. In some cases, it may be appropriate to repeat abnormal ECGs to rule out technical factors contributing to ECG artifacts or abnormality. It is important that leads are placed in the same positions each time for consistency. The overall conclusion with the interpretation of the ECGs will be recorded on the appropriate CRF. The interpretation of the ECGs will be recorded as normal, abnormal but not clinically significant, or abnormal and clinically significant. QTc will be calculated using Fridericia's correction formula.

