4.5.1 Randomization

Subjects will be randomized in a 1:1 ratio to either the AKST1210 column (the investigational treatment) or to control (no column). The study will be performed using a manual randomization process. Subjects will be randomized at Visit 2.1, after eligibility has been confirmed (including Day –14 to –1 Run-In). Subjects who discontinue or are unblinded may be replaced. Subjects who withdraw or are withdrawn during screening will be replaced. Replacement subjects will receive the same treatment as the original subjects. Subjects who have been unblinded will not be replaced.

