5.8.8 Weight

Weight will be collected as described in the Schedule of Events, Protocol Section 15.1. Observed values in lb. will be tabulated at pre-HD and post-HD per HD session. Change from pre-HD at post-HD per HD session will also be summarized (included in DSMB report). A listing of weight (lb.) will be provided.

The initial fluid removal goal, actual fluid removal, amount differs from the goal, the proportion of subjects achieved the fluid removal goal will also be summarized by visit and treatment period. Actual fluid removal = total fluid output - total fluid intake. The amount differs from the goal = actual fluid removal – fluid removal goal.

5.8.9 12-lead ECG

A 12-lead ECG will be performed to obtain Heart rate (beats/min), QT interval (msec), and QT interval corrected by the Fridericia formula (QTcF (msec)). ECGs will be collected at Visit 1 and Visit 6 EOS.

Observed value at baseline and Visit 5, along with the change from baseline value at Visit 5 will be summarized (included in DSMB report).

A Shift table, by ECG test and by overall interpretation from Visit 1 to Visit 6 EOS will be provided.

A listing of all 12-lead ECG will be provided. A listing of abnormal 12-lead ECG will also be provided.

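### Two SAP rules are wrong as written: the numeric ECG change summary is set at a visit with no ECG, and the inch-to-centimetre conversion for BMI is inverted

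*SAP*

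**What the plan says.** **ECG (SAP 5.8.9, 12-lead ECG).** The measures are numeric: "A 12-lead ECG will be performed to obtain Heart rate (beats/min), QT interval (msec), and QT interval corrected by the Fridericia formula". The timing is explicit: "ECGs will be collected at Visit 1 and Visit 6 EOS". The next paragraph then specifies: "Observed value at baseline and Visit 5, along with the change from baseline value at Visit 5 will be summarized (included in DSMB report"). The sentence after that sets a shift table from Visit 1 to Visit 6, and listings of all ECGs and of abnormal ECGs follow.

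**BMI (SAP 5.4.1, Demographics).** BMI is 10,000 times weight in kg over height in cm squared. For height: "If height is collected in inches, it will be converted to cm by dividing the value by 2.54". For weight: "If weight is collected in pounds, it will be converted to kg by dividing the value by 2.205". BMI is summarized by arm and in total for the ITT population. Continuous demographic variables are compared between arms with a Wilcoxon rank-sum test, as a check on the randomization. Protocol 5.1 limits entry to "Body mass index (BMI) ≥ 20 and ≤ 36".

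**The concern.** In the ECG section, the visit named for the numeric summary is not one of the two visits at which the same section collects ECGs. Change from baseline in ECGs is a secondary endpoint (Protocol 4.2.2, SAP 3.2), and Protocol 7.1.1.1.4 has QTc calculated by Fridericia's formula, so a continuous QTc is part of the protocol and not only of the SAP. SAP 5.8 says that the DSMB tables are identified within each analysis description. In 5.8.9 only the Visit 5 sentence carries that mark. Programmed literally, the one ECG table tagged for the DSMB would hold baseline values and no scheduled follow-up.

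In the BMI rule, an inch is 2.54 cm, so centimetres are obtained by multiplying. Dividing makes the height too small, and BMI then squares the error. At stake is the BMI row of the baseline table and its rank-sum comparison.

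**Working it through.** **ECG: the places side by side**

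- SAP 5.8.9, collection: Visit 1 and Visit 6 EOS.
- SAP 5.8.9, numeric summary: baseline and Visit 5.
- SAP 5.8.9, shift table: Visit 1 to Visit 6.
- SAP 4.7: Visit 5 is End of Treatment (Week 12, Day 82) and Visit 6 is EOS (Week 14). They are separate visits, so this is not two names for one visit.
- SAP 5.1: the ECG baseline is Screening.
- Protocol 15.1.1: 12-lead ECG marked at Screening. Protocol 15.1.2 to 15.1.4: no ECG row. Protocol 15.1.5: ECG marked under Visit 6 only.
- SAP 5.6: missing data are not imputed.

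Scheduled ECGs at Visit 5 are therefore 0, against one per attending subject at Visit 6. Only an unscheduled ECG could put a value in the Visit 5 cells.

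**BMI: size of the error**

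Inputs: the BMI formula and the two conversion rules from SAP 5.4.1; 1 in = 2.54 cm; the eligible range 20 to 36 from Protocol 5.1.

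1. The BMI formula is sound: 80 kg and 170 cm gives 10,000 × 80 / 170² = 27.68, the same as 80 / 1.70².
2. The weight rule is sound: 1 / 2.205 = 0.4535 kg per lb, against 0.4536.
3. Height rule as written: h/2.54. Correct: h × 2.54. The height is too small by 2.54² = 6.45.
4. BMI ratio, as written to correct: (h × 2.54)² / (h / 2.54)² = 2.54⁴ = 41.62, whatever the height or weight.
5. Example (assumed subject, 68 in and 80 kg). As written: 10,000 × 80 / (68/2.54)² = 1116. Correct: 10,000 × 80 / (68 × 2.54)² = 26.8.
6. The eligible range would print as 20 × 41.62 = 832 to 36 × 41.62 = 1498.

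**BMI: effect on the baseline row**

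- All heights in cm: the rule never runs and the effect is zero.
- All heights in inches: every BMI is multiplied by the same constant. Mean, SD, median and range are all 41.6 times too large. The ranks, and so the rank-sum p-value, do not change.
- Mixed units: each inch-recorded subject moves above every cm-recorded one, so the ranks are distorted and the mean and SD are meaningless. As an illustration, assume 13 subjects in an arm, all with true BMI 27, and one height in inches: mean = (12 × 27 + 27 × 41.62)/13 = 111.4, SD 304, median still 27.
- Type I error of the rank-sum test under mixed units: Protocol 7.1.1.1.3 says "Height will be measured at Screening; weight will be measured at Screening and throughout the study", and SAP 4.5.1 says "Subjects will be randomized at Visit 2.1, after eligibility has been confirmed". The unit is therefore fixed before the arm is known and cannot depend on it, so the error rate is essentially unchanged.

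**The case against.** The best case on the other side is that both slips would be caught. A BMI of 832 or more cannot pass output review in a trial that caps entry at 36. The ECG slip sits between two sentences that name the right visits. SAP 5.1 allows modifications, with deviations noted in the CSR. The table shells are separate attachments that are not part of these documents, so what would actually be programmed is unknown. The DSMB's data elements are to be defined under its charter (Protocol 8.6, SAP 4.9), and blinded ECG data are reviewed through the study by the CRO's medical monitor and/or the sponsor's program physician (Protocol 8.6).

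Most of this stands, and it is why the point is minor. It does not make the text right. These are pre-specified rules, and under SAP 5.1 a departure made quietly in programming would itself have to be reported as a deviation.

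On BMI it is also fair that height may be in centimetres throughout. The documents do not say. All sites are in the US, the SAP writes a rule for inches, and SAP 5.8.8 tabulates weight in pounds. Inches are therefore realistic but not established.

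**Conclusion.** Both rules are wrong as written, and the point is minor.

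- **ECG:** certain on the face of the documents. The numeric summary for a listed secondary endpoint, in the only ECG output that 5.8.9 marks for the DSMB report, has zero scheduled post-baseline values.
- **BMI:** a 41.6-fold overstatement for each height recorded in inches, conditional on inches being used and on the rule being programmed literally. It is confined to one row of the ITT baseline table. No model, population definition, efficacy analysis or safety analysis uses BMI.

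A reader might infer more, and the documents do not support it:

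- *That ECG follow-up is lost.* The Visit 6 ECG is still collected, and the shift table and listings still report it.
- *That the DSMB will see no ECG data.* Only the marking in 5.8.9 is known. The charter, which defines what the DSMB receives, is not among these documents.
- *That the rank-sum p-value for BMI is invalid.* It is unchanged if all heights are in inches. With mixed units the ranks are distorted, but the type I error is essentially unchanged.
- *That eligibility is corrupted.* SAP 5.4.1 is an analysis derivation. Eligibility is confirmed before randomization, and nothing ties it to this rule.
- *That the safety conclusions are affected.* The primary endpoint is the incidence of TEAEs and SAEs, and neither rule enters it.

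**What to change.** **SAP 5.8.9:** in the numeric summary sentence, replace Visit 5 with Visit 6 EOS in both places, so that it agrees with the collection visits, the shift table and Protocol 15.1.5. Keep the DSMB marking.

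**SAP 5.4.1:** in the height sentence, change the operation so that inches are converted to centimetres by multiplying by 2.54. Leave the pounds-to-kg sentence as it is, since it is correct.

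Check the table shells and derivation programs for the same two slips. The cost is two wording corrections in a SAP revision before unblinding, with no new data, visits or analyses.
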